The following measurements are derived: (i) the sensory thresholds for gas, first desire to defecate, urgency, and pain during ascending method of limits, (ii) the sensation score (gas, urgency, and pain) in response to the four phasic distensions (12, 24, 30 and 36 mmHg above BOP), and (iii) rectal compliance.

The sequential proportionate volumes (observed volume/maximum observed volume) will be used to obtain a pressure corresponding to half the maximum observed volume using a computer-based linear interpolation algorithm.⁵⁵ Thus, the summary value for each compliance curve will be calculated from the pressures corresponding to the volumes just above and just below the half maximum volume. This provides the specific pressure ($Pr\ 1/2$) corresponding to one half of the maximum observed volume, for each participant, where a smaller $Pr\ 1/2$ corresponds to higher rectal compliance.

STATISTICAL ANALYSIS

A. *Clinical Data*

- a. **Abdominal pain score:** the average pain score each day, as measured by the 100 mm VAS, over the treatment period will be calculated and compared between groups using an unpaired analysis (t test or rank sum test if not normally distributed). The averages during run-in 2-week period will be available to conduct analysis using the baseline measurement as covariates.
- b. **Clinical scales for depression, quality of life** (HADS and IBS-QOL). These summaries will be obtained from measurements made at baseline, at the end of treatment, and 4 weeks after treatment ends.

In addition to calculating these summaries, demographic and other information, including participant age and gender, as well as other medications will be recorded for each participant and summarized as appropriate for the type of data.

Treatment success for chronic pain is defined as a 30% decline in subjective pain ratings on visual analog scales for the treatment group compared to the placebo treatment group. An “Intent to Treat” data analysis will be used given the possibility that some participants will not be able to complete the study. Descriptive statistical analysis and unpaired t-tests (or rank sum test) will be used.

B. *Physiological Data*

Colonic Transit

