A “time to event” approach (i.e. pressure required to evoke specific sensations) will be used to assess four sensation thresholds (first desire to defecate, gas, urgency, and pain). Since some threshold levels are “censored” (e.g. pain not evoked by the maximum distension pressure used according to the protocol approved by the IRB), a Kaplan-Meier summary of the pressure thresholds will be used to univariately depict the cumulative probability of evoking the sensation, and proportional hazards regression models will be used to assess group effects separately for each of the sensation types. The same covariates listed above used in the analyses of sensation VAS ratings will be included in the proportional hazards regression models, in particular the ratings of “tiredness”, “peace”, “worried”, and “activity” recorded during the sensation studies.

Rectal compliance

The covariates included in the ANCOVA models for fasting colonic tone and compliance $Pr \frac{1}{2}$ values will be age, gender, BMI, the “tiredness”, “peace”, “worried”, and “activity” scores, the HAD scores, and the BDQ somatic symptom score.

Endpoints

Primary Endpoint

is abdominal pain scores in participants with non-constipation IBS

Summary of Secondary Endpoints will be focused on characterizing rectal compliance and sensation, and colonic transit,

The *secondary endpoints* for analysis will be:

- a. Colonic transit geometric center at 24 hours
- b. Colonic transit geometric center at 48 hours
- c. Gastric emptying of solids $T_{1/2}$ (minutes) and % emptied at 4h
- d. Rectal compliance
- e. Rectal sensation during ascending method of limits
- f. Rectal sensation during random order, graded phasic distensions
- g. IBS-QOL
- h. Safety/adverse effects

Sample Size

This study is meant to be a pilot study that will provide preliminary information regarding the usefulness of treating participants chronic abdominal pain associated with non-constipation IBS with rimegepant.

The estimated effect size (with $n=12$ per treatment group) for each of the primary and secondary endpoints is based on power calculation using data acquired from patients with IBS-D at Mayo Clinic^{56, 57}.

Table 4. Key Gastrointestinal Physiologic Data in 163 People Based on Bowel Function Subgroup

	Healthy controls	IBS-C	IBS-D	IBS-M
Number of males	41 (0)	49 (0)	44 (3)	29 (0)
Fasting gastric volume, mL	226 ± 11	229 ± 11	247 ± 11	222 ± 12
Postprandial gastric volume, mL	736 ± 13	740 ± 14	735 ± 14	770 ± 17

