Δ postprandial fasting gastric volume, mL	511 ± 13	525 ± 12	488 ± 12	548 ± 19 ^a
Proportion of GE at 2 h	0.47 ± 0.02	0.49 ± 0.02	0.45 ± 0.02	0.42 ± 0.03
GE, T1/2, min	126.0 ± 4.4	126.8 ± 4.7	135.5 ± 5.6	137.6 ± 6.0
Satiation: maximum tolerated volume, mL	1028 ± 44	1044 ± 40	1046 ± 45	1106 ± 81
Satiation: aggregate symptom score	158 ± 14	186 ± 10	188 ± 12	184 ± 16
Colonic filling at 6 h, %	48 ± 5	54 ± 4	56 ± 3	44 ± 5
Colon transit GC 24 ^b	2.35 ± 0.16	2.03 ± 0.10	3.03 ± 0.19	2.34 ± 0.10
Colon transit GC 48 ^c	3.23 ± 0.18	3.0 ± 0.13	4.14 ± 0.17	3.94 ± 0.16
Rectal compliance, Pr _{1/2} , mm Hg	12.6 ± 0.8	12.5 ± 0.8	14.2 ± 0.6	14.0 ± 0.9
Threshold for first sensation, mm Hg	7.8 ± 0.5	7.8 ± 0.7	8.4 ± 0.7	8.1 ± 0.8
Threshold for gas, mm Hg	13.8 ± 1.5	14.0 ± 1.2	13.3 ± 1.2	14.5 ± 1.6
Threshold for pain, mm Hg	29.1 ± 2.1	29.0 ± 2.0	31.0 ± 1.8	31.0 ± 2.2
Threshold for urgency, mm Hg	17.5 ± 1.1	20.5 ± 1.6	18.8 ± 1.4	17.4 ± 1.2
Sensation rating, pain 30 mm Hg	55.1 ± 4.5	52.5 ± 4.6	55.3 ± 4.2	54.3 ± 5.6
Sensation rating, urgency 30 mm Hg	74.9 ± 2.8	71.5 ± 3.3	74.4 ± 2.5	74.3 ± 3.1

NOTE. There were 41 controls and 122 patients with IBS (data are mean ± SEM). For the number of participants undergoing each measurement, see the Methods section.

^aP = .017 versus healthy controls.

^bOverall P < .001.

^cOverall P < .001.

In a prior study that evaluated abdominal pain scores on a daily diary 0-100 mm for severity of abdominal pain, patients with IBS had the following pain severity at baseline prior to treatment (Pain, 100-mm VAS 37.2 (27.1–49.5) (57)

parameter	Mean	SD	Effect size (absolute and % of mean), 80% power; α=0.05
Average pain score on 0-100mm VAS	37.2	11	13.16 (35%)
Colonic transit GC24	3.03	1.25	1.5 (50%)
Colonic transit GC48	4.14	1.12	1.34 (32%)
Rectal compliance	14.2	3.94	4.7 (33%)
Threshold for first sensation	8.4	4.59	5.5 (65%)
Threshold for gas	13.3	7.87	9.4 (71%)
Threshold for pain	31	11.81	13.3 (43%)
Threshold for urgency	18.8	9.18	11 (59%)
Sensation rating pain 30 mmHg	55.3	27.55	33 (60%)
Sensation rating urgency 30mm Hg	74.4	16.4	19.6 (26%)
Gastric emptying T1/2	135.5	36.7	44 (32.6%)
Proportion of gastric emptying at 4h	0.45	0.13	0.156 (34.7%)

FEASIBILITY AND TIME FRAME

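### The primary pain comparison is an unadjusted test with an unstated normality switch, and the plan does not commit to adjusting for the run-in pain it already collects

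*Combined protocol and SAP*

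**What the plan says.** Under Statistical Analysis, A. Clinical Data, item a, each participant's average daily VAS pain over the treatment period is "compared between groups using an unpaired analysis (t test or rank sum test if not normally distributed". No normality test or threshold is given. The next sentence reads: "The averages during run-in 2-week period will be available to conduct analysis using the baseline measurement as covariates". It gives no model and does not say whether such an analysis is primary, supportive or optional. The same section later repeats the unadjusted choice without any covariate: "Descriptive statistical analysis and unpaired t-tests (or rank sum test) will be used".

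The Endpoints section says only that the primary endpoint "is abdominal pain scores in participants with non-constipation IBS", so item a is the only place where the primary test is defined. The run-in text under Study Participants has pain recorded daily for two weeks before randomization and requires a score of at least 30 mm for entry. The planning table under Sample Size, headed "Effect size (absolute and % of mean), 80% power; α=0.05", gives 13.16 mm (35%) for average pain. By contrast, the sections on colonic transit, sensory ratings, thresholds and rectal compliance, all secondary endpoints, specify covariate models.

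**The concern.** Run-in and treatment-period pain are multi-day averages of the same daily scale in the same people, so they may well be correlated. If they are, adjusting for the run-in mean removes predictable between-patient variation. It also removes the effect of a chance difference in starting pain, which can be sizeable with 12 per arm. The plan collects what is needed but does not commit to using it for the primary result.

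The plan also leaves the primary result open. The choice between t test and rank sum depends on the observed distribution, with no rule. A covariate-adjusted result may be produced beside them with no stated rank. If the three disagree, nothing in the text says which one answers the primary aim.

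**Working it through.** **Inputs.** From Sample Size: 12 per arm, SD 11 mm, mean 37.2 mm, α = 0.05, 80% power. From A. Clinical Data: a 30% success threshold, which on the planning mean is 0.30 × 37.2 = 11.16 mm. Assumption: r, the correlation between run-in mean and treatment-period mean, shown from 0 to 0.7.

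**Step 1: the plan's own figure.** The standard error of the unadjusted difference is 11 × √(2/12) = 4.49 mm. A two-sided t test on 22 df (noncentral t) reaches 80% power at 13.165 mm, and power at 13.16 mm is 79.97%. The one-sided version gives 11.53 mm. The stated 13.16 mm is therefore the unadjusted two-sided t test and takes no credit for baseline pain.

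**Step 2: adjusted power.** ANCOVA residual SD = 11 × √(1 − r²). The standard error is multiplied by √(1 + 1/20) for estimating the slope, with 21 df. At r = 0.5: 11 × 0.866 = 9.53; × √(2/12) = 3.89; × 1.025 = 3.99 mm. Then 11.16 / 3.99 = 2.80, which gives 76% power.

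**Step 3: the entry threshold.** As an approximation, take run-in mean pain as normal (mean 37.2, SD 11) truncated at 30 mm. Its SD falls to 8.0 mm. The residual SD does not change, so ANCOVA power hardly moves. The total SD shrinks to √(r² × 8.0² + (1 − r²) × 11²), so the unadjusted test improves. At r = 0.7 this is √(31.4 + 61.7) = 9.65 mm. The last two columns come from 40,000 simulated trials per setting.

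| r | Unadjusted | ANCOVA | ANCOVA detectable difference (80% power) | Unadjusted, truncated | ANCOVA, truncated |
|---|---|---|---|---|---|
| 0 | 66% | 64% | 13.5 mm | 66% | 64% |
| 0.3 | 66% | 68% | 12.9 mm | 68% | 68% |
| 0.5 | 66% | 76% | 11.7 mm | 71% | 76% |
| 0.6 | 66% | 82% | 10.8 mm | 74% | 82% |
| 0.7 | 66% | 90% | 9.7 mm | 77% | 90% |

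Power is at 11.16 mm. In the truncated columns r is the correlation before truncation.

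**Step 4: chance imbalance.** At SD 11 the difference in baseline means has a standard error of 4.49 mm, and a gap above 5 mm arises in about 27% of randomizations. With baseline truncated, the standard error is 8.0 × √(2/12) = 3.3 mm and the figure is about 13%. About r times the gap enters the unadjusted estimate: 0.5 × 5 = 2.5 mm at r = 0.5.

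**Step 5: freedom of choice.** In simulation without truncation, the t test and ANCOVA each hold about 5% type I error and the rank sum test stays just under it. If the most favourable of the three were reported, the error would be about 7% at r = 0.3, 8% at 0.5 and 9% at 0.7. At a true effect of 11.16 mm, the t test and ANCOVA disagree on significance in about 10%, 17% and 27% of trials at those values.

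**The case against.** The strongest defence is that the plan foresees baseline adjustment with the right covariate, that the named t test is valid and matches the sizing exactly, and that this is a pilot. All of that stands. A reader might infer that the run-in data are thrown away. The text does not support this, because adjustment is provided for but left without a model or a rank.

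A reader might also infer that the unadjusted estimate is biased or its test invalid. It is not. Over randomizations the estimate is unbiased, type I error is about 5%, and only about r times a baseline gap carries over.

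A third tempting reading starts from the success definition, "Treatment success for chronic pain is defined as a 30% decline in subjective pain ratings", and argues that comparing treatment-period levels cannot address a decline. That fails. The definition is relative to placebo, and under randomization the difference in levels has the same expectation as the difference in change. ANCOVA targets that same difference.

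The gain also rests on an r that is not in the documents. At r = 0.3 it is about 2 points without truncation and nil with it, and near r = 0 there is a small loss. The normality switch alone does little harm: simulated type I error with it was 5.3% for normal data and 5.4% to 6.1% for skewed data. What survives is that the adjusted analysis has no status, the switch has no rule, and the choice can change the conclusion.

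**Conclusion.** The point holds as a gap in commitment and specification, not as an error of validity. If r is 0.5 to 0.7, naming ANCOVA raises power at 11.16 mm from 66% to between 76% and 90%. Allowing for the entry threshold, the comparison is 71% against 76% up to 77% against 90%. At r of 0.3 or less the precision argument is weak, and the case rests on having one pre-specified primary result.

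These figures assume normal data, SD 11 mm, equal SDs before and during treatment, 12 analysed per arm, and truncation of the run-in mean at exactly 30 mm. The documents do not say whether SD 11 already describes patients who meet the entry threshold; if it does, the untruncated columns are the closer guide.

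A reader might expect adjustment to make up for an SD that is too small. If the unlabelled range in "Pain, 100-mm VAS 37.2 (27.1–49.5" is an interquartile range, the SD is about (49.5 − 27.1) / 1.349 = 16.6 mm. Power at 13.16 mm is then about 46% unadjusted, and 55% (r = 0.5) to 72% (r = 0.7) adjusted, still short of 80%. For a pilot this should be fixed, but the trial does not stand or fall by it.

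**What to change.** Before unblinding, replace the test wording in A. Clinical Data, item a, and the repeat of it later in that section. Name one primary analysis: ANCOVA of each participant's mean daily VAS pain over the treatment period on treatment group, with the 2-week run-in mean as covariate, reporting the adjusted difference and its 95% confidence interval. Keep the unadjusted t test and the rank sum test as pre-specified sensitivity analyses, and delete the normality-based switch. Reporting the residual SD and the observed r would also serve the stated aim of informing the variance for a later trial.

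The cost is a sentence or two of wording and one degree of freedom, with no new data. If r proves to be near 0, about 2 to 3 points of power are lost (66% to 64% in the calculation above).

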Secondary aims of this study are:

- #1: To describe the effect of rimegepant on rectal compliance in participants with non-constipation IBS and chronic abdominal pain.
- #2: To evaluate the effects of rimegepant on rectal sensation based on ascending method of limits and on graded rapid phasic distensions in participants with non-constipation IBS and chronic abdominal pain.
- #3: To evaluate effects of rimegepant on overall colonic transit in participants with non-constipation IBS and chronic abdominal pain.
- #4: To evaluate safety of rimegepant in participants with non-constipation IBS and chronic abdominal pain.

METHODS

STUDY INTERVENTION AND CONCOMITANT THERAPY

Rimegepant

Rimegepant (Nurtec ODT®) is an oral, small molecule, CGRP receptor antagonist approved in the US for the acute treatment of migraine and the preventive treatment of episodic migraine in adults. This is a summary of the pharmacology and dosing of rimegepant in the proposed study:

- Approved Formulation – oral dissolving tablet (ODT)
- Dosing as per Migraine Prevention: 75 mg Every Other Day (EOD) for 4 weeks/28-32 days
- Pharmacokinetics: Tmax: 1.5h; $t_{1/2}$: 11h; bioavailability: 64%
- Drug-drug Interactions: Avoid strong CYP3A4 inducers and strong or moderate CYP3A4 inhibitors
- Hepatic and Renal Impairment: Avoid use in severe hepatic impairment and end stage renal disease
- Notable Adverse Events: nausea (2.7% in rimegepant group vs 0.8% in placebo group); abdominal pain/dyspepsia (2.4% in rimegepant group vs 0.8% in placebo group)

Description of Study Drug

Rimegepant is supplied as a 75 mg white to off-white ODT in a pre-filled blister card containing 8 tablets. The placebo is supplied as a 75 mg white to off-white ODT in a pre-filled blister card containing 8 tablets. Blister cards are to be stored at 15-25°C (59-77°F).

Blinding

Participants will be blinded to their assigned study intervention. Investigators and other site staff will be blinded to participants' assigned study intervention. Participants will be assigned to receive study intervention according to the assigned treatment group from the randomization scheme. Investigators will remain blinded to each participant's assigned study intervention throughout the course of the study.

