The covariates to be considered for inclusion in the ANCOVA models for colonic transit are gender, BMI, HAD scores (anxiety and depression scales), the BDQ Somatic Symptom Checklist (SSC) score. These will be considered for inclusion by checking plots of residuals (from the ANCOVA models) against these scores. The analysis will compare colonic transit between the two treatment groups.

Gastric Emptying

Given the reports of nausea and vomiting in participants with migraine as well as observations of these symptoms during clinical trials of CGRP receptor antagonists, we will also measure gastric emptying $T_{1/2}$ (minutes) and proportion emptied at 4h (%) at the end of 4 weeks treatment and compare the results for the active treatment group to those of the placebo group. Sex and BMI will be considered as co variates in this analysis.

Sensory Ratings

The assessment of phenotype associations with observed sensory ratings (rectal sensation VAS scores) will be based on analysis of covariance (ANCOVA) for repeated measures (the four phasic distension levels). Each type of VAS score will be analyzed individually (first sensation, gas, urgency, and pain). The covariates to be included in the ANCOVA models for each VAS score were age, sex, BMI, the “tiredness”, “peace”, “worried”, and “activity” VAS scores, the HAD scores, and the BDQ SSC score. Though most of these scores may not be significant covariates in these models, due to the nature of the responses, it is appropriate to include them. In addition, the corresponding pressure (12, 24, 30, 36 mmHg) at each phasic distension level (the repeated factor) is included in each of these ANCOVA models along with the main effect term for phenotype (e.g. age, sex, BMI), and the 2-way interaction term for phenotype by pressure.

Sensation pressure thresholds

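### Colonic-transit covariates are to be chosen from plots of outcome residuals, which can raise the per-endpoint false-positive rate from 5% to about 5-7%

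*Combined protocol and SAP*

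**What the plan says.** Under Statistical Analysis, part B, the Colonic Transit paragraph names five candidate covariates: gender, BMI, HAD anxiety, HAD depression and the somatic symptom checklist score. On how they get into the model it says: "These will be considered for inclusion by checking plots of residuals (from the ANCOVA models) against these scores". The next sentence is: "The analysis will compare colonic transit between the two treatment groups". The paragraph sets no cut-off and no fallback model. It does not state whether treatment is in the model that yields the residuals, or whether the check precedes unblinding.

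The neighbouring models are handled differently. For the sensory ratings the covariates go in even though most are not expected to be significant. The threshold models reuse that list, and the compliance model has its own stated list. (The gastric-emptying paragraph also leaves sex and BMI open, but ties the choice to no outcome plot.)

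Secondary aim 3 is a single question: "To evaluate effects of rimegepant on overall colonic transit in participants with non-constipation IBS and chronic abdominal pain". The secondary endpoints answer it twice, once with the geometric center at 24 hours and once with "Colonic transit geometric center at 48 hours". Neither is ranked above the other and no multiplicity rule is given. The table under Sample Size is headed "Effect size (absolute and % of mean), 80% power; α=0.05" and gives each time point its own row.

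**The concern.** Whether a covariate enters should not depend on how this trial's outcomes scatter within the two arms. If treatment is in the residual model, the covariates kept are those that happen to track the within-arm scatter. The residual mean square then falls by more than the lost degrees of freedom account for, while the true variability of the treatment estimate does not fall to match. The final p-value is read as though the model had been set in advance, so it is somewhat too small.

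If the residuals come from a model without treatment, the choice uses outcomes and covariates but not the assignment. With no drug effect, the same covariates would be kept whatever the allocation, and the test keeps its level. The size of the problem therefore turns on a detail that the plan leaves out.

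The protocol calls the effect of this drug class on transit unknown, names inhibition of colonic motility as a potential effect, and intends to use its data to plan a controlled trial. A transit difference that depends on how a plot was read is weak input to that planning.

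**Working it through.** **Inputs from the documents.** 12 per arm ("The estimated effect size (with $n=12$ per treatment group) for each of the primary and secondary endpoints"); alpha 0.05 and 80% power per row of the table; SD 1.25 at 24 hours and 1.12 at 48 hours; five candidate covariates.

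**Inputs not in the documents, taken as assumptions.** The strictness of the visual check, expressed as a p-value screen on the correlation between covariate and residual; the share of outcome variance that the covariates explain (0 or 0.3); the correlation between the two time points (0 to 0.9).

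**Step 1: reproduce the plan's figures.** For a two-sample t test the detectable difference is d = λ × SD × √(2/n). With 22 degrees of freedom, two-sided 0.05 and 80% power, λ is about 2.93, and √(2/12) = 0.408.
- 24 hours: 2.93 × 1.25 × 0.408 ≈ 1.50 (plan: 1.5; power 80.2%).
- 48 hours: 2.93 × 1.12 × 0.408 ≈ 1.34 (plan: 1.34; power 80.0%).

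A one-sided t test would give 88% power, so the rows are two-sided tests at 0.05, one for each time point.

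**Step 2: one endpoint, no drug effect, 24 participants.** Each simulated trial fits the first model, screens the five covariates against its residuals, refits with those kept, and tests treatment at 0.05. There were 15,000-20,000 trials per setting, with a simulation error of about 0.2 points.

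| Residuals from | Screen | Variance explained | False positives per endpoint |
|---|---|---|---|
| model with treatment | p<0.05 | 0 | 5.9-6.2% |
| model with treatment | p<0.20 | 0 | 6.8-7.1% |
| model with treatment | p<0.05 | 0.3 | 7.1-7.2% |
| model with treatment | p<0.20 | 0.3 | 6.7-7.0% |
| model without treatment | p<0.05 or p<0.20 | 0 or 0.3 | 4.7-5.3% |
| no screening, all five forced in | none | 0 or 0.3 | 4.8-5.2% |

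With treatment in the residual model, a stricter screen at p<0.01 gave as little as 5.1%. Hence about 5-7% overall.

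**Step 3: at least one of the two endpoints falsely significant.** With fixed covariates and independent endpoints this is 1 − 0.95² = 9.75%. The other values are simulated.

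| Correlation of 24 h and 48 h | Covariates fixed | Screened at p<0.05 to p<0.20, treatment in residual model |
|---|---|---|
| 0 | 9.75% | 12.0-13.9% |
| 0.5 | 9.1% | 11.2-12.8% |
| 0.7 | 8.5% | 10.1-11.8% |
| 0.8 | 7.9% | 9.7-11.2% |
| 0.9 | 7.1% | 8.6-10.1% |

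At correlation 0.7, having two endpoints adds 8.5 − 5.0 = 3.5 points, and screening adds a further 10.1 − 8.5 = 1.6 to 11.8 − 8.5 = 3.3 points. At correlation 0.75 a p<0.01 screen gave as little as 8.4% for the pair, little above the unscreened value. Without treatment in the residual model, the pair stays at 7.1-10.2% across correlations 0 to 0.9.

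**Step 4: are there two endpoints?** The Study Design section puts the baseline scans at 6-8 and 24 hours, with the rectal test after the 24-hour image. The methods for physiological endpoints put the rectal test after a 48-hour scan. The endpoint list and the sample-size table both include 48 hours, so two endpoints are probably meant. If only 24 hours is measured, Step 3 falls away and the rate is about 5-7%.

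**The case against.** The strongest reply is that the text is loose rather than wrong. It sets no numerical screen, so any inflation figure rests on one supplied from outside. An analyst who adds a covariate only for an obvious pattern behaves like a strict screen and may do almost no harm. The text also does not say outright that treatment is in the residual model, and without it the inflation disappears. All of this stands, and it is why the result is a conditional range. It does not remove the point. The residuals are said to come from the ANCOVA models, and those models exist to compare the two arms, so treatment in the model is the natural reading.

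A second reply is that these are openly listed secondary endpoints of a self-described pilot, that many other secondary measures are equally unadjusted, and that 0.05 is applied row by row. This also stands. No section promises 5% for aim 3, so the 7-10% for the pair describes the design and breaks no commitment. Requiring one deciding time point would be a preference.

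A reader might also count 2⁵ = 32 possible covariate sets and infer that the smallest p-value among them could be reported, which would give about 10-11% for one endpoint. The plan does not describe that: covariates are judged on residual plots, not on the treatment p-value.

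**Conclusion.** The point holds as a minor one. Choosing transit covariates from residuals of a model with treatment makes the treatment test mildly anti-conservative: about 5-7% per endpoint instead of 5%. This assumes treatment in the residual model and a visual check equivalent to a screen between p<0.01 and p<0.20. Without treatment in that model there is essentially no inflation.

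The two unranked time points are a separate matter. They give about 7-10% for at least one false transit effect with covariates fixed, and about 9-14% with screening at p<0.05 to p<0.20, over correlations from 0.9 to 0.

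A reader might infer that the error for aim 3 is 10-11% where the plan claims 5%. The documents do not support that. The figure is one part of the range, it needs an inclusion threshold and a correlation that are not given, and the 5% is per endpoint. Nor do they support the inference that a transit slowing would be treated as confirmed, since the protocol describes its results as preliminary.

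**What to change.** - Delete the residual-plot inclusion rule from the Colonic Transit paragraph.
- Name one short covariate set for the transit ANCOVA before unblinding, and use it at both 24 and 48 hours. This brings transit into line with the sensory, threshold and compliance models. With covariates fixed, the simulated rate per test was 4.8-5.2% even with all five forced in, so the reason for a short list is to save degrees of freedom, not to protect the error rate.
- Keep residual plots as model diagnostics, and put other covariates in sensitivity analyses only.
- Optionally, say which time point leads for aim 3, or label both exploratory. If a joint error rate is wanted, 0.025 for each gives 4.9% if they are independent, and 4.7% down to 3.4% for correlations from 0.5 to 0.95.
- Reconcile the scan times in the Study Design section with those in the methods for physiological endpoints, because they decide whether there are two transit endpoints.

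The cost is one or two sentences in the statistical section. The downside is that a covariate later seen to be prognostic could enter only a sensitivity analysis.

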Figure shows experimental procedure for measurement of rectal compliance by ascending method of limits (AML), sensation thresholds (indicated by arrows) and sensation ratings by random order pressure distensions and recording symptoms using 100mm visual analog scales

Ascending method of limits: compliance and sensory thresholds

Rectal sensory thresholds and compliance are measured by ramp inflation, increasing in steps of 4 mm Hg for 1 minute per step from 0 to a maximum 60 mm Hg. Thresholds for gas, first desire to defecate, urgency, and pain are indicated by the study participants by pressing a button at the distension pressure at which sensations are perceived. Ramp inflation is

terminated as soon as participants reported the first sensation of pain.

The bag is deflated and BOP is determined by pressure in the bag increased from 4 mm Hg in steps of 2 mm Hg for 1 minute per step until respiratory excursions are observed. The baseline operating pressure (BOP) set 2 mm Hg above the minimal distension pressure at which respiratory excursions are clearly recorded from the barostat tracing. Once BOP is determined there is another rest for 10 minutes.

Random order phasic distensions: sensory ratings

Phasic distensions of 12, 24, 30 and 36 mm Hg above BOP are each applied once in random order, (the order being provided before the start of the study by the biostatistician), with the participants blinded to the distension order. Each distention is maintained for 60 seconds with an interval between distensions of 2 minutes with the balloon deflated to BOP. Distension pressure is associated with intensity ratings that are generally proportional to the magnitude of the distension pressures.⁵²⁻⁵⁴ Participants mark three separate 100 mm visual analog scales (VAS) 30 seconds after the onset of the distension for the sensations of gas, urgency, and pain. These scales are anchored at each end by the descriptions 'unnoticeable' and 'unbearable'. Pressure is immediately released if the participant reported greater than 80 mm of pain on the VAS scale and higher distensions are not subsequently administered. During the assessment of sensation, the interaction between the participant and the study investigator is kept to a

minimum. Participants will also complete another VAS questionnaire to describe their sense of tiredness, peace, worry and activity before the first measurement of sensation.

Data analysis for compliance and sensory endpoints

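### The pain-threshold row of the sample-size table has about 75% power, not the stated 80%, and three labels in the rectal analysis plan do not match what the barostat test records

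*Combined protocol and SAP*

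**What the plan says.** **Power figures.** Under Sample Size, the plan introduces "The estimated effect size (with $n=12$ per treatment group) for each of the primary and secondary endpoints". The table that follows has a column headed "Effect size (absolute and % of mean), 80% power; α=0.05". Its pain-threshold row reads mean 31, SD 11.81, effect 13.3 (43%).

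**Phasic distensions.** Under Random order phasic distensions, the protocol states: "Participants mark three separate 100 mm visual analog scales (VAS", one each for gas, urgency and pain. The section on data analysis for compliance and sensory endpoints lists the same three as the derived sensation scores. The statistical section on Sensory Ratings then says: "Each type of VAS score will be analyzed individually (first sensation, gas, urgency, and pain".

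**Ramp (ascending method of limits).** The derived measures are "the sensory thresholds for gas, first desire to defecate, urgency, and pain during ascending method of limits". Sensation pressure thresholds, in the statistical section, plans to analyse the same four by proportional hazards regression. The sample-size table instead has a row "Threshold for first sensation" (mean 8.4, SD 4.59, effect 5.5) and none for first desire to defecate.

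**Tone.** The statistical paragraph on Rectal compliance begins: "The covariates included in the ANCOVA models for fasting colonic tone", and goes on to the compliance summary. The barostat section places the bag in the rectum only.

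**The concern.** There are two separate problems.

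The first is numerical. One row of a table built on a single rule departs from that rule, and it does so in the favourable direction: the pain threshold is credited with more sensitivity than 12 per arm provides. Rectal sensation is a secondary aim, and the protocol says the pilot is meant to inform the planning of a later controlled trial, so the planning figures should be right.

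The second is a mismatch of labels. An analyst following the text would find no data for a first-sensation rating or for fasting colonic tone, and would have to drop or replace both without written authority. The table also leaves it unclear whether first desire to defecate, which is recorded and analysed, has a planning figure.

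**Working it through.** **Inputs.** From Sample Size: 12 per arm, 80% power, alpha 0.05, and the SD and effect in each row. The sidedness of alpha is not stated, so it is tested below.

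**Step 1: find the table's rule.** For a two-sample t test with 12 per arm there are 22 degrees of freedom, and the noncentrality parameter is (effect/SD) × √(12/2). Solving for 80% power at two-sided 0.05 gives effect/SD = 1.197. Applied to every row:

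| Row | SD | Stated effect | Stated/SD | 1.197 × SD | Power at stated effect |
|---|---|---|---|---|---|
| Average pain VAS (primary) | 11 | 13.16 | 1.196 | 13.17 | 80.0% |
| GC24 | 1.25 | 1.5 | 1.200 | 1.50 | 80.2% |
| GC48 | 1.12 | 1.34 | 1.196 | 1.34 | 80.0% |
| Rectal compliance | 3.94 | 4.7 | 1.193 | 4.72 | 79.7% |
| First-sensation threshold | 4.59 | 5.5 | 1.198 | 5.49 | 80.1% |
| Gas threshold | 7.87 | 9.4 | 1.194 | 9.42 | 79.8% |
| **Pain threshold** | **11.81** | **13.3** | **1.126** | **14.13** | **75.1%** |
| Urgency threshold | 9.18 | 11 | 1.198 | 10.99 | 80.1% |
| Pain rating, 30 mmHg | 27.55 | 33 | 1.198 | 32.97 | 80.1% |
| Urgency rating, 30 mmHg | 16.4 | 19.6 | 1.195 | 19.63 | 79.9% |
| Gastric emptying T1/2 | 36.7 | 44 | 1.199 | 43.92 | 80.1% |
| Gastric emptying proportion | 0.13 | 0.156 | 1.200 | 0.156 | 80.2% |

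Eleven rows reproduce; the pain threshold does not.

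**Step 2: the pain-threshold row.** 13.3/11.81 = 1.126 SD, noncentrality 1.126 × √6 = 2.76, power 75.1%. The 80% figure is 1.197 × 11.81 = 14.1 mmHg, and 14.13/31 = 45.6%. The printed 43% is 13.3/31 = 42.9%, so the percentage carries the same error. At 13.3 mmHg, 13 per arm gives 78.7% and 14 per arm gives 81.8%.

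**Step 3: could another convention explain it?**
- Normal approximation: 78.8% for this row, still below 80%, and 83.2% to 83.6% for the other rows. It is not the table's method.
- One-sided t test: 84.8% for this row and about 88% for the others. It is not the table's method either.
- A misprinted SD: 13.3 would need an SD of about 11.11. But Table 4 gives an SEM of 1.8 for IBS-D, and 1.8 × √43 = 11.80; the table's other SDs also correspond to an n of about 43. With the 44 printed for IBS-D in Table 4, the SD is 11.94 and power is 74.1%. The SD looks right and the effect wrong.

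**Step 4: labels side by side.**

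| Item | Recorded | Analysis planned | Row in effect table |
|---|---|---|---|
| First-sensation VAS rating | No | Yes (Sensory Ratings) | No |
| Fasting colonic tone | No | Yes (Rectal compliance) | No |
| First-sensation threshold | Not under that name | Not under that name | Yes |
| First-desire-to-defecate threshold | Yes | Yes | Not under that name |

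**The case against.** The strongest reply is that very little depends on any of this. The gap between 13.3 and 14.1 mmHg is 0.8 mmHg on a ramp that moves in 4 mmHg steps. It concerns one secondary measure in a declared pilot of fixed size, and no success rule uses it. Fasting colonic tone appears once, in a sentence about covariates; it is not an aim, a derived measure or a listed endpoint. Analyses that cannot be run bias nothing. All of that stands, and it limits the weight of the point without removing the errors.

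A second reply is that 75% is not the power of the planned analysis either. Thresholds will be analysed by proportional hazards regression with censoring and covariates, and the table's t test only approximates that. This also stands, so any restated figure should carry the caveat.

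A reader might go further and infer that the plan both analyses and powers several rectal quantities it never measures. The documents do not support that. No single item is both: the first-sensation rating and colonic tone have analyses but no planning row, and the first-sensation threshold has a planning row but is not among the thresholds analysed. Colonic tone is not a rectal parameter.

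Nor do the documents show that the threshold behind the first-sensation row goes unmeasured. The label sits where first desire to defecate would be expected and may simply be loose wording for it. Table 4 puts first sensation (8.4 mmHg) below gas (13.3 mmHg) in IBS-D, so the match cannot be assumed. But no value for first desire to defecate is given, so it cannot be excluded. That reading would not rescue the first-sensation rating, because first desire to defecate is not rated on a VAS either.

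**Conclusion.** The concern holds as a minor correction. By the method that reproduces the other 11 rows, the pain-threshold effect of 13.3 mmHg has 75% power, and the effect detectable with 80% power is 14.1 mmHg (46% of 31). This assumes a two-sided t test, 12 evaluable participants per arm, no dropout and the table's own SD. Two planned analyses, the first-sensation rating and fasting colonic tone, name variables that the protocol does not collect. One planning row carries a label that the ramp does not use, and whether it means first desire to defecate cannot be settled from the documents.

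A reader might take the power error as a fault in the sample size or the primary comparison. It is neither: the primary-endpoint row gives 80.0%.

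**What to change.** - **Sample Size, pain-threshold row:** restate the effect as 14.1 mmHg (46%), or keep 13.3 mmHg (43%) and state 75% power. Add that the threshold figures are t-test approximations to the planned proportional hazards analysis.
- **Sensory Ratings:** delete first sensation from the list of VAS scores, leaving gas, urgency and pain.
- **Rectal compliance (statistical section):** delete fasting colonic tone.
- **Sample Size, first-sensation row:** confirm whether it is meant as first desire to defecate. If so, relabel it. If not, delete it and state that first desire to defecate has no planning figure.

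A new ramp response should not be added to suit a table label. It would change the measurement procedure, and anyone already tested would lack it (the documents do not say whether anyone has been).

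The cost is wording only. The one downside is that a stated secondary-endpoint figure becomes slightly less favourable.
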